### **Randomization:**

Participants will be randomly assigned to either 1) Vector NIV followed by SOC NIV or 2) SOC NIV followed by Vector NIV. Randomization will be generated via a randomization website. For the SOC NIV therapy, participants will be required to use a Vector Device in place of their current NIV device. The Vector therapy will not be enabled, and the device will be set according to their current SOC NIV prescription.

**Cohort 1 (NIV Current Users):** Participants in Cohort 1, regardless of randomized therapy order, will be required to undergo the Vector device titration at study visit 2. (Appendix A) For the participants randomized to SOC NIV first, the settings determined from the Vector device during the randomization visit will then be applied when they cross over to Vector NIV at visit 3.

**Cohort 2 (NIV Naïve):** Participants in Cohort 2, regardless of randomized therapy order, will be required to undergo the Vector device titration at study visit 2. (Appendix A) Participants in cohort 2 who were randomized to SOC NIV first will have previously been titrated to SOC NIV therapy at visit 1.

Initiation of the Vector NIV titration will take place under the supervision of the study investigator, research coordinator and / or healthcare professional (Respiratory Therapist, Sleep Technician, etc.). Appendix A outlines the protocol and device settings that will be used for the Vector device titration. For the participants in Cohort 2 that are initially randomized to SOC arm, clinical study staff will follow currently established NIV standard of care titration protocols. After successful completion of the Vector NIV titration, participants will be given one-on-one operational instructions on the device by clinical study staff. They will also be given a user manual, mask, and tubing and be asked to use the device at home for 4 to 6 weeks. For the participants in Cohort 2 that are randomized to SOC arm, they will continue to use the Vector device as they did during the 2-week home acclimation period with the previously determined SOC NIV settings.

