## **V. Study Design:**

This will be a prospective, randomized, pilot study with cross-over design.

Patients who meet inclusion criteria will be randomized in a 1:1 ratio to receive either standard of care (SOC) NIV (control) or Vector (Active) for the first 4 to 6-week treatment period, followed by the other treatment during the second 4 to 6 weeks (see Figure 1). There will be two different patient cohort groups, patients that are current users of NIV and patients that are Naïve to NIV.

(Figure 1)

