### A. Schedule of Events:

#### Screening Procedures:

##### Study Participation Screening (Prior to Visit 1)

Participants will be contacted by designated study staff from Temple University Lung Center Research Team. Participants may be pre-screened through medical records over the phone to determine eligibility. A screening script will include a general review of key inclusion and exclusion criteria. Participants that are interested will be scheduled for the screening visit at the clinical office.

Upon screening, study participants will be divided into 2 different cohorts – current NIV users and participants that are Naïve to NIV therapy.

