### **NIV SOC Titration (NIV Naïve Cohort only)**

Participants who are NIV naïve and determined to have EFL with a titrated EPAP >6cmH2O will then undergo standard SOC titration (Appendix A) in order complete a 2 week NIV acclimation period. Initiation of SOC titration will take place under the supervision of the study investigator, research coordinator and / or healthcare professional (Respiratory Therapist, Sleep Technician, etc.).

After successful completion of the device titration, participants will be given one-on-one operational instructions on the Vector device by clinical study staff. The Vector therapy will not be enabled. The device will be set up with the optimal pressures determined from the SOC titration. In addition to the application of the settings determined by the SOC titration, the Automated Airway Management (AAM) feature will be enabled with the minimum set EPAP to 4 cmH2O and a maximum of 20 cmH2O. This feature will adjust the EPAP to maintain upper airway patency.

The purpose of the 2 week NIV acclimation period is to determine if the patients that are naïve to NIV will adhere to therapy and also if they potentially have underlying OSA that require 90% EPAP pressures higher than the determined EFL titrated EPAP at the screening visit. After receiving training on the device, participants will also be given a user manual, mask, and tubing and be asked to use the device at home for 2 weeks.

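### No blocking or cohort stratification is specified for therapy order, and the planned analysis has no term to correct a chance imbalance within the NIV-naive cohort

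*Combined protocol and SAP*

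**What the plan says.** Section V (Study Design) sets the ratio: "Patients who meet inclusion criteria will be randomized in a 1:1 ratio". The Randomization paragraph names the two orders, "Participants will be randomly assigned to either 1) Vector NIV followed by SOC NIV or 2) SOC NIV followed by Vector NIV", and then the method: "Randomization will be generated via a randomization website". Nothing is said about list type, block size, stratification factors or concealment.

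The same section defines two populations: "There will be two different patient cohort groups, patients that are current users of NIV and patients that are Naïve to NIV". Membership is settled before randomisation at visit 2, because at screening "study participants will be divided into 2 different cohorts". No size or quota is given for either cohort. Naive participants are titrated to standard-of-care NIV at visit 1 and are then to "be asked to use the device at home for 2 weeks" before being randomised.

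Section XI (Primary Analysis) compares the two therapies as paired samples, by paired t-test or Wilcoxon signed-ranks test, with no term for period, sequence or cohort. General Considerations rules out sensitivity analyses. The Withdrawal text in section VI aims for 30 completers from an estimated 50 enrolled.

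**The concern.** In a two-period crossover each person serves as his or her own control. That removes differences between people, but not a change between period 1 and period 2 that would occur on either therapy. With equal numbers in the two orders such a change cancels; with unequal numbers part of it is counted as a therapy effect.

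The cohorts are unlikely to share one period effect. Current users must already average more than 4 hours of NIV a night, while naive participants enter period 1 with two weeks' experience. Telephone contact also differs by period (Phone Follow-ups): in period 1 it is daily for a week and then weekly, in period 2 daily for the first week only. The calls are partly meant to encourage use, and usage is a secondary endpoint. No washout is described.

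What matters is therefore balance of order within each cohort. Balance overall does not secure it, and one pooled period term does not fully repair its absence. At stake is the accuracy of the PaCO2 difference in the single trial that will be run, whose results may be used to power a pivotal trial.

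**Working it through.** **Inputs from the plan:** two orders, 1:1; 30 completers; unadjusted paired test.

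**Assumptions, because the plan gives no figure:** 10 to 20 naive among the 30; simple randomisation; naive period effect p (period 2 minus period 1) of 2, 3 or 5 mmHg; zero period effect in current users; paired SD of 4, 6 or 8 mmHg. The plan has no power calculation to reproduce.

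**Model.** Let d = Vector minus SOC and tau = the true difference. In a cohort with period effect p, the expected d is tau - p for Vector-first and tau + p for SOC-first. Hence:

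- Paired mean: bias = p x (naive SOC-first - naive Vector-first) / N.
- Single period term: bias = (p_naive - p_current)/2 x (naive share of SOC-first - naive share of Vector-first).
- Period plus period-by-cohort terms: bias = 0.

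**Chance of a 2:1 or worse naive split (exact binomial):** 34% (n=10), 39% (n=12), 30% (n=15), 12% (n=20).

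**Bias for given splits (Vector-first:SOC-first), as a fraction of p:**

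| Naive | Current | Paired test | Single period term | Period-by-cohort |
|---|---|---|---|---|
| 4:8 | 9:9 | 4/30 = 0.133 | (8/17 - 4/13)/2 = 0.081 | 0 |
| 4:8 | 11:7 | 0.133 | (8/15 - 4/15)/2 = 0.133 | 0 |
| 5:10 | 10:5 | 5/30 = 0.167 | (10/15 - 5/15)/2 = 0.167 | 0 |
| 4:8 | 6:12 | 0.133 | (8/20 - 4/10)/2 = 0 | 0 |

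Rows 2 and 3 are balanced 15:15 overall and still biased. In both, adding a cohort main effect to the period term leaves the bias unchanged (0.133 and 0.167). In row 4 both cohorts are split 1:2, and a single period term suffices.

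**Spread over simple randomisations (simulation, N = 30).** The 95th percentile of absolute bias, as a fraction of p:

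| Naive n | Paired test | Single period term |
|---|---|---|
| 10 | 0.20 | 0.18 |
| 12 | 0.20 | 0.19 |
| 15 | 0.23 | 0.18 |
| 20 | 0.27 | 0.18 |

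The mean bias is zero. For the paired test these percentiles are 0.20 x 2 = 0.4 to 0.27 x 2 = 0.5 mmHg if p = 2, 0.6 to 0.8 if p = 3, and 1.0 to 1.3 if p = 5.

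**Type I error (12 naive + 18 current, all SDs and p values above).** Over randomisations it is 4.6% to 5.6% for every analysis. Given naive 4:8 and current 11:7, it is 5.0% to 5.6% for the paired test and 5.0% to 8.4% with a single period term; the maximum is at SD 4 and p = 5.

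**What allocation can do.** With 10 to 20 naive participants and a single period term, the SD of the bias is about 0.09 of p under simple randomisation and also about 0.09 under unstratified blocks of 4. Cohort-stratified blocks of 4 bring it to 0.015 to 0.026.

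**Limits of stratified blocks (paired test, sizes 2 and 4 mixed).** The maximum bias is 1/30 = 0.033 of p for cohorts of 15+15, but 2/30 = 0.067 for 14+16. If 18+18 are randomised and 15+15 complete at random, the 95th percentile is 0.10 and the largest value seen 0.17.

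**The case against.** Several points on the other side stand.

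- A reader might infer that allocation is simple and unstratified. The plan does not say so; the website could use either device. What can be said is that neither is specified, and the probabilities above hold only if allocation is simple.
- A reader might also infer that the trial is biased in a known direction or that its test is invalid. It is not: the error averages zero, and unconditional type I error stays near 5%.
- The naive period effect may be small. PaCO2 is measured at the end of each period, when naive participants have had 2+4 to 2+6 = 6 to 8 weeks of NIV, then 2+4+4 to 2+6+6 = 10 to 14 weeks. Only drift between those two points counts. Acclimation and the 4-hour usage rule at visit 2 remove some early change.
- Zero drift in current users widens the gap between cohorts. If the cohorts share one period effect, a single period term removes the bias entirely.
- Sampling error is larger. With SD 4 to 8 mmHg the 95% half-width at N = 30 is 2.045 x 4/√30 = 1.5 to 2.045 x 8/√30 = 3.0 mmHg.
- The absence of any period term in the planned test is the larger gap, and a period-by-cohort term would correct the bias in this model without touching the randomisation.

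These points limit the size and certainty of the problem. They do not supply a safeguard: the plan has none in allocation, and none in the stated analysis.

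**Conclusion.** The point holds as an unspecified allocation method combined with an unadjusted analysis. Under simple randomisation a lopsided naive cohort is an ordinary event. The resulting conditional bias would then seldom exceed about a quarter of the naive period effect with the planned test, or about a fifth with a single period term. That rests on 10 to 20 naive among 30 completers and no period effect in current users. Any figure in mmHg depends on a period effect that the plan does not give.

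It is an avoidable loss of precision and a conditional bias in the one trial that will be run. Severity is minor to moderate for a single-site pilot without a power calculation. It deserves action mainly because prevention costs almost nothing.

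**What to change.** 1. In the Randomization paragraph, state that the website generates the two orders in permuted blocks of randomly mixed size (for example 2 and 4), separately for current users and naive participants, with the next assignment concealed from staff who enrol. Blocking without stratification by cohort would not address the point.
2. In Primary Analysis, analyse the within-person differences with period and period-by-cohort terms. This is needed even with stratified blocks, because losses after randomisation can undo the balance. Name the interaction explicitly, since a cohort main effect alone does not remove the bias.
3. Report the numbers in each order by cohort, both randomised and completing.

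The cost is a website setting, a few sentences and a few degrees of freedom out of about 30. Block ends become slightly predictable at a single site where no masking is described; mixed block sizes limit this.

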### **Phone Follow-ups:**

Participants will be sent home with the Vector device with their randomized therapy. During the initial week, the participant will be contacted daily to determine if there are any problems with the device and to encourage compliance. Participants will be asked to use the Vector device at night for the following 6 weeks. Participants will then be contacted weekly from week 2 to the last week of their take home period (maximum of 6 weeks). During the second take home period, all participants will be called daily during the first week only.

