### Secondary Objectives:

- To evaluate treatment effect of Vector on overall quality of life
- To evaluate treatment effect of Vector on sleep quality
- To evaluate treatment effect of Vector on physical activity levels
- To Evaluate treatment effect of Vector on Ventilator collected parameters
- To Evaluate treatment effect differences on nocturnal SpO2 and PaCO2 or TcCO2

**Endpoints:**Primary Endpoint:

Daytime CO2 levels at the end of 4-6 weeks of therapy as determined by Arterial Blood Gas (PaCO2)

Secondary Endpoints:

- Average daily device usage
- Therapy Comfort and Preference
- Incidence of Unanticipated Serious Adverse Device Effects (USADEs) and Serious Adverse Events (SAEs) for the Vector vs. the control group.

Exploratory Endpoints:

- Changes in quality of life scores ((CAT) SGRQ, dyspnea ratings mMRC),
- Ventilator collected parameter differences after 6 weeks of use (Respiratory Rate (RR), Minute Ventilation (MV))
- Sleep Quality differences as measured by PSG and actigraphy
- Changes in activity levels (mean and max activity counts)

**Study Population:** Approximately 30 COPD patients with chronic hypercapnia and evidence of expiratory flow limitation will be included.  
**Phase:** Pilot study

**Sites/Facilities Enrolling Participants:** Temple University Hospital

**Description of Study Intervention:** NIV with Auto Adjusting EPAP

**Study Duration:** Approximately 12 months

**Participant Duration:** Approximately 15 weeks

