## **Study Visit 4 (Overnight Sleep Study - within 4 to 6 weeks of visit 3)**

Participants will be asked to report to the sleep lab for the second overnight sleep study at a scheduled date and time. The sleep testing will begin near the subject's usual bedtime and end at approximately 6 A.M.

Prior to the sleep study with the therapy device, the trained technologists will verify mask size, fit, and adjustment that was determined at study visit 1. Details of the PSG set up can be found in the standard procedures section of the protocol.

Morning ABG, Therapy Comfort and QOL assessments: Following the completion of the sleep study (morning after), all participants will have to return to the research center where their activity monitors will be downloaded, fill out study related questionnaires as well as have their ABGs collected. Details on ABG collection and study questionnaires can be found in the standard procedures section of the protocol.

In the event that participants are unable to come into the research clinic for visit 3 or 4, remote administration of questionnaires via telephone or direct mail may be conducted. Participants may be asked to return their device SD cards via direct mail using a provided postage-paid envelope.

Procedures														
	Determine eligibility	Enrollment/Baseline		Visit 1 (day 0)		Visit 2 Daytime Titration		Week 1: Daily Check-in Calls		Weeks 2-6: Weekly Check-in Calls	Week 4: Diary Reminder Call 1	Visit 3 Overnight PSG study	Week 1: Daily Check-in Calls	Week 4: Diary Reminder Call 2
Chart Review	X													
Informed consent		X												
H&P , demographics		X												
QoL Questionnaires			X							X			X	
EFL assessment	X													
Morning ABG										X			X	
In Lab Sleep Study (PSG)										X			X	
Device titration (NIV Current)			X											
Device Titration (NIV Naïve)		X	X											
Clinical follow up (assess patients concerns/issues with device, mask, or other)										X	X		X	
Actigraphy set up/ data download		X								X			X	
Device data download (NIV Current)										X			X	
Device data download (NIV Naïve)				X										
Sleep Diary Reminder								X			X			
Side effects and AE assessment				X	X	X	X	X	X	X	X	X	X	

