### **Actigraphy Measurements & Sleep Diary**

Actigraphy is a method of measuring activity and sleep which is achieved by wearing a small watch-like device for an extended period of time. Most units contain an accelerometer and continually record the movement it undergoes. These data are later read to a computer for analysis. These data will provide an objective record of physical activity and sleep / wake patterns throughout the 6 weeks of home use.

The wrist-worn actigraph device will provide a continuous measure of both how much the participant has slept during the night and how active they are during the day. There is an event button that the participant will be asked to press when the participant is in bed, near asleep and also upon awaking.

Participants may be asked to keep a sleep diary during the last two weeks of each arm of the study in order to supplement the actiwatch data. The study team will call the participant to remind them to start using the diary.

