### **Adverse Event Assessment and Follow-Up**

Adverse events will be collected on an ongoing basis following signing of informed consent. Detailed information regarding the event will be recorded on the appropriate form in the electronic case report form (eCRF), where the Investigator will determine the severity of the event, relationship to study product (assessed only by those with the training and authority to make a diagnosis), and time of resolution/stabilization of the event. Follow-up data to ascertain the existence of residual effects from the event will be obtained. Serious adverse events must be reported to the sponsor within 24 hours of discovering the occurrence of the SAE. The research staff is required to complete and submit the sponsor's standard SAE form detailing the event.

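### Weekly check-in calls run throughout the first take-home period but are dropped after week 1 of the second, so safety prompting and compliance support differ by period

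*Combined protocol and SAP*

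**What the plan says.** Section V, Phone Follow-ups, describes the first take-home period in two steps. In week 1, "During the initial week, the participant will be contacted daily to determine if there are any problems with the device and to encourage compliance". After that, "Participants will then be contacted weekly from week 2 to the last week of their take home period (maximum of 6 weeks". For the second period the same paragraph says "During the second take home period, all participants will be called daily during the first week only".

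The schedule of events table, printed after Study Visit 4, largely agrees. Its column for weekly check-in calls in weeks 2-6 appears once, before Visit 3, and has no counterpart afterwards. The table does add one later contact in the second period, "Week 4: Diary Reminder Call 2". This fits the Actigraphy Measurements & Sleep Diary section: "Participants may be asked to keep a sleep diary during the last two weeks of each arm of the study".

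The table row "Side effects and AE assessment" is marked without a break to the last column. On that reading, the check-in calls, both diary calls and both sleep-study visits are adverse-event contacts. The table layout is broken in the available text, so the column positions are inferred.

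Section IX adds: "Adverse events will be collected on an ongoing basis following signing of informed consent". The synopsis lists as a secondary endpoint: "Incidence of Unanticipated Serious Adverse Device Effects (USADEs) and Serious Adverse Events (SAEs) for the Vector vs. the control group".

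**The concern.** Minor effects such as mask discomfort, dryness or gastric insufflation are the ones most likely to go unrecorded when nobody asks. Section XVIII says they are all to be recorded. If the scheduled asking thins out in the second period, fewer such events will be found there, whichever therapy is in use.

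The calls also have a stated compliance purpose. The protocol attaches it to the daily calls of week 1 and gives the weekly calls no separate purpose, so it is reasonable, though an inference, to read it across. Usage hours are a secondary endpoint and better adherence is part of the study hypothesis, so a drop in contact could also lower usage in period 2.

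The Primary Analysis in section XI compares therapies as paired samples (paired t-test, Wilcoxon signed-ranks or McNemar) with no period or sequence term, so nothing in the analysis would absorb such a difference.

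**Working it through.** The documents give no total number of contacts to reproduce. The counts below come from Phone Follow-ups and the schedule table.

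**Contacts per period.** Let w be the period length in weeks (4 to 6).

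- Period 1 check-in calls: 7 + (w − 1), which is 10, 11 or 12 for w = 4, 5 or 6.
- Period 2 check-in calls: 7 for any w.
- Fall: 1 − 7/10 = 30% at 4 weeks; 1 − 7/12 = 42% at 6 weeks.
- Adding one diary call and one sleep-study visit to each period: 12 versus 9 at 4 weeks (25% fewer) and 14 versus 9 at 6 weeks (36% fewer).
- After week 1 only, on the same count: 5 versus 2 at 4 weeks, 7 versus 2 at 6 weeks.

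**Longest gap in period 2.** Daily calls end on day 7 and week 4 covers days 22-28. The gap to the diary call is therefore 22 − 7 = 15 to 28 − 7 = 21 days. In a 6-week period the gap from that call to day 42 is 42 − 28 = 14 to 42 − 22 = 20 days. Both are about 2-3 weeks. If the diary call is not made, the gap runs from day 7 to Visit 4: 28 − 7 = 21 to 42 − 7 = 35 days.

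**Contacts by therapy, 30 completers.** With n1 Vector-first and n2 SOC-first, mean contacts on Vector are (n1·c1 + n2·c2)/30. SOC has n1 and n2 exchanged. Here c2 = 9, and c1 = 12 (4 weeks) or 14 (6 weeks).

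| Split | Vector/SOC, 4 weeks | Vector/SOC, 6 weeks |
|---|---|---|
| 15:15 | 10.50/10.50 = 1.00 | 11.50/11.50 = 1.00 |
| 18:12 | 10.80/10.20 = 1.06 | 12.00/11.00 = 1.09 |
| 20:10 | 11.00/10.00 = 1.10 | 12.33/10.67 = 1.16 |

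Under simple randomisation (an assumption, since no block scheme is described), a split of 18:12 or worse in either direction has probability 0.36, and 20:10 or worse 0.10.

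**Effect on recorded events (illustration).** The capture rates are assumed: 90% in a called week, d = 50-80% in an uncalled week, with true event rates equal on both therapies. Week 4 of period 2 counts as called.

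- Period 1 capture: e1 = 0.9.
- Period 2 capture: e2 = (2/w)·0.9 + (1 − 2/w)·d.
- Lowest, w = 6 and d = 0.5: e2 = 0.300 + 0.333 = 0.633, so r = e2/e1 = 0.70.
- Highest, w = 4 and d = 0.8: e2 = 0.450 + 0.400 = 0.850, so r = 0.94.

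The spurious Vector/SOC event ratio is (n1 + n2·r)/(n2 + n1·r):

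- 15:15: 1.00 for any r.
- 18:12: 29.33/29.00 = 1.01 (r = 0.944) to 26.44/24.67 = 1.07 (r = 0.704).
- 20:10: 29.44/28.89 = 1.02 to 27.04/24.07 = 1.12.

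If SOC-first completers are in excess, the ratios invert.

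**Usage.** If usage is δ hours lower in period 2, the paired Vector-minus-SOC difference shifts by +δ in Vector-first and −δ in SOC-first participants. The mean shift is δ(n1 − n2)/30: zero at 15:15, 0.20δ at 18:12, 0.33δ at 20:10. Even at 15:15 the opposite shifts add spread to the paired differences. The documents give no value for δ.

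**The case against.** Three stronger readings are tempting, and the documents do not support them.

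- A reader might infer that adverse-event contact ends after week 1 of period 2. Phone Follow-ups alone suggests this. But it is the schedule table that makes the calls adverse-event contacts, and the same table marks the week-4 diary call and the final visit as such. Adverse events are also collected continuously from consent, and unscheduled calls and visits are documented.
- A reader might infer a built-in bias between Vector and SOC. Order is randomised 1:1 and the analysis compares therapies, not periods. SOC-first participants have Vector in the less-observed period, and Vector-first participants have SOC there. With balanced sequences the therapy ratio is 1.00.
- A reader might infer that the secondary safety endpoint is compromised. It covers only USADEs and SAEs, and nothing shows that capture of a death or a hospital admission depends on a weekly call. Section IV lists other reported adverse events as exploratory, and the Safety Analysis plans only listings.

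It is also fair to say that this is an unpowered pilot and that the capture rates above are assumed.

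These arguments limit the size of the problem but do not remove it. The fall in contact is explicit and unexplained. Balance is not assured: no blocking is described, and the plan expects about 50 enrolled for 30 completers without saying how much of that loss follows randomisation. Anyone who leaves in or after period 1 contributes only closely monitored time on the first therapy.

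**Conclusion.** The point holds as an avoidable period effect, and correcting it is a cheap improvement. Planned check-in calls are 30-42% fewer in period 2, or 25-36% fewer when the diary call and end-of-period visit are counted.

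The consequence is probably lower capture of non-serious events in period 2 and possibly lower usage. It biases Vector versus SOC only if sequences or post-randomisation dropout are unequal. On the assumed capture rates that bias is modest at 18:12 and at most about 12% at 20:10.

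The conclusion rests on three things: the inferred reading of the table's adverse-event row, the week-4 call actually being made, and capture rates that the documents neither give nor exclude. The text and the table also disagree on whether any call follows week 1 of period 2.

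**What to change.** In Phone Follow-ups and in the schedule table, set the same call schedule for both take-home periods, daily in week 1 and weekly to the end, with the same adverse-event and side-effect prompt at each call. Planned calls then become 10 versus 10 (4 weeks) or 12 versus 12 (6 weeks), and contact is equal between therapies for completers with equal period lengths, whatever the sequence split. In the same edit, reconcile the statement that second-period calls are confined to week 1 with the week-4 call in the table.

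Where period 2 has already been run, report adverse events and usage by period and sequence as well as by therapy, and keep every reported event. These are descriptive tabulations and do not conflict with the statement in section XI that no sensitivity analysis will be done.

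The cost is 3-5 short calls per participant by staff who already make them in period 1 (3 × 30 = 90 to 5 × 30 = 150 calls for 30 completers), one revised sentence and one table edit. The downside is slightly more site time and participant contact.
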